**b Introduction:**

Hypertension (HT) is an important risk factor for stroke, coronary heart disease (CHD), heart failure and renal diseases, and the leading risk factor of global disease burden. A multitude of interventions have proven efficacy in lowering blood pressure and reducing long term HT complications, including pharmacologic treatment, DASH diet (Dietary Approaches to Stop Hypertension), exercise, weight reduction, smoking cessation, alcohol moderation and self-monitoring of blood pressure. A few studies had examined the effects of coordinated multidisciplinary management programmes for HT patients to maximize the effectiveness of these interventions, but the long term benefit or cost-effectiveness of such programmes are uncertain.

In Hong Kong, over 200,000 patients with HT are being managed in public primary care clinics (i.e. General Out-patient Clinics (GOPCs) and Family Medicine Clinics (FMC)) under the Hospital Authority (HA); but more than 45% HT patients have still not achieved target blood pressure control (HA Internal communication). In order to improve the quality of care for patients with uncontrolled HT at GOPCs, the evidence-based , structured protocol-driven multidisciplinary Risk Assessment and Management Programme – Hypertension (RAMP-HT) was launched since October 2011 by the HA with the support from the Food and Health Bureau. Standardized cardiovascular risk factor assessment, hypertensive complication screening and assessment on patient adherence to treatment are carried out on enrolled patients (Appendix A). Patients are stratified into low,

medium or high risk groups according to the 10-year cardiovascular disease (CVD) risk calculated from their relevant risk factors by the Joint British Society 2005 Equation. A multidisciplinary team comprised of doctors, nurses, dieticians, physiotherapists and/or occupational therapists would then deliver individualized management targeted to the patient's risk factors according to standardized risk-stratified guidelines (Appendix B).

In our evaluation of quality of care of RAMP-HT as part of the Extended Study on Evaluation of Quality of Care of Chronic Disease Management and Public-Private Partnership Programmes of the HA (HMRF Reference no: EPC\_HKU-2), we have found that, among patients whose baseline blood pressure was not controlled ( $\geq 140/90\text{mmHg}$ ), RAMP-HT patients had significantly greater reduction in mean systolic blood pressure (SBP), low-density lipoprotein cholesterol (LDL-C) and estimated 10-year CVD risk after 12 months than matched HT patients receiving usual care from GPs ( $p<0.001$  for all parameters). In addition, a significantly greater proportion of patients in the RAMP-HT group achieved target blood pressure (i.e.  $\text{SBP/DBP}<140/90\text{mmHg}$ ) after 12 months compared to usual care group; the Number Need to Treat (NNT) for achieving one more target blood pressure was 14. These preliminary findings on improvement in blood pressure and CVD risks are very encouraging, suggesting that RAMP-HT may be effective in preventing cardiovascular and renal complications in primary care HT patients.

### **c Aim, objectives and Hypotheses:**

Aim and objectives:

The aim of this study is to evaluate the cost-effectiveness of the RAMP-HT of the HA in primary care patients with uncontrolled hypertension.

The objectives are to

1. Evaluate the long term (5-year) effectiveness of RAMP-HT compared to usual care in reducing cardiovascular complications, end-stage renal disease and all-cause mortalities in a cohort of primary care patients with uncontrolled hypertension at baseline
2. Estimate the direct medical cost of RAMP-HT and other health services

among primary care HT patients with or without complications

3. Evaluate the cost-effectiveness of RAMP-HT, compared to usual care, in gaining one Quality-Adjusted Life Year (QALY) in primary care patients with uncontrolled hypertension

Hypotheses:

1. RAMP-HT is more effective in reducing 5-year cardiovascular complications, end stage renal disease and all-cause mortality among primary care patients with uncontrolled hypertension compared to usual care
2. The direct medical cost of RAMP-HT patients, for the same disease complication status, is not higher than that of usual care except for the RAMP-HT cost
3. The direct medical cost of HT patients with one or more complications is higher than that of HT patients without any complication
4. RAMP-HT is cost-effective compared to usual care, i.e. the incremental cost-effectiveness ratio (ICER) per QALY gained is below the threshold value of 1 annual GDP (Gross Domestic Product) per capita of Hong Kong (HK\$295,303, 2013), which is the benchmark recommended by the World Health Organization

#### **d Plan of Investigation:**

##### **(i) Study design**

A retrospective study on public primary care population-based matched cohorts of patients with uncontrolled hypertension in Hong Kong

##### **(ii) Subjects**

All patients who have enrolled into the RAMP-HT between 1 Oct 2011 and 31 March 2012, fulfilled the following inclusion criteria and without any exclusion criterion will be included in the RAMP-HT cohort. The same number of matched patients receiving usual care in GOPCs who have never enrolled into RAMP-HT on or before 31 March 2017, fulfilled the following inclusion criteria and without any exclusion criterion will be randomly selected from the HA clinical management system (CMS) to form the usual

care cohort.

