#### Inclusion criteria

1. Age  $\geq 18$  years old and  $<80$  years old
2. Coded with ICPC-2 of K86 on or before baseline\* (\*date of RAMP-HT enrolment for RAMP-HT cohort, and 31 March 2012 for usual care cohort)
3. Had uncontrolled blood pressure (i.e. average Systolic Blood Pressure (SBP)  $\geq 140$  mmHg OR Diastolic Blood Pressure (DBP)  $\geq 90$  mmHg between 6 months before and 3 months after baseline\*)

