#### *Sample size calculation*

- a. For the long-term effectiveness evaluation, the difference in 5-year incidence of CVD between the RAMP-HT and usual care group is the primary outcome. From the result of our RAMP-HT QOC study, the observed 1-year incidence of CVD in the RAMP-HT and usual care group was 1.33% and 1.76% respectively. A conservative estimate of the 5-year incidence of CVD in RAMP-HT and usual care group would be 7% and 8%, respectively. A minimum sample size of 7,116 subjects from each group will be needed to detect a difference of 1% in incidence rates of CVD between RAMP-HT and usual care group with 90% power and at 5% level of significance.

We have identified from the HA CMS data set of the RAMP-HT QOC study 8,681 eligible RAMP-HT patients and 8,681 usual care patients who fulfilled the inclusion criteria and without any exclusion criterion matched by propensity score matching. These two matched cohorts will be the subjects of this long-term effectiveness and cost-effectiveness

study. The flow chart of subject selection is attached in Appendix C.

- b. For the costing analysis, 140 subjects from each of the RAMP-HT and usual care groups will be required to show that the direct medical costs of RAMP-HT patients (excluding RAMP cost) is not higher than that of usual care HT patients by independent one side t-test with 0.3 effect size and 80% power at 5% significance level.

307 RAMP-HT and 291 usual care patients had been recruited from May 2013 to March 2014 in GOPCs across Hong Kong for the longitudinal evaluation of patient reported outcomes (PRO) in the RAMP-HT QOC study. These patients will be follow-up from May 2015 to March 2016 as part of our RAMP-HT QOC study; telephone survey on private health service utilization will be conducted at the same time. Taking 25% attrition rate into account, 230 RAMP-HT and 218 usual care patients will complete the questionnaire. This sample will be adequate for the comparison of private medical cost between RAMP-HT and usual care group.

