**HA CMS Data Extraction of Incidence of HT Complications and All-cause Mortality**

Our RAMP-HT QOC study will have collected anonymous 3-year follow up HA CMS data of the cohorts available by November 2015. This study plans to extend the follow up period for an additional 2 years to measure the 5-year incidence of CVD, ESRD and mortality outcomes of these HT patient cohorts from 1 Oct 2011 to 31 March 2017. The data extraction will be carried out by the HA statistics team. Each patient in the cohorts (RAMP-HT and usual care groups) will be observed from baseline to the first occurrence of any of the outcome events until 31 March 2017, with CMS documented diagnoses defined by the relevant ICPC-2 and ICD-9-CM codes below:

1. Cardiovascular disease (CVD) is defined as the presence of any of coronary heart disease (CHD), heart failure or stroke. CHD includes all ischaemic heart disease, myocardial infarction (MI), coronary death or sudden death as indicated by the ICPC-2 K74 to K76 or ICD-9-CM 410.x, 411.x to 414.x, 798.x codes. Heart failure is defined as the ICPC-2 K77 or ICD-9-CM 428.x codes. Stroke (fatal and non-fatal stroke) is defined by the ICPC-2 K89 to K91 or ICD-9-CM 430.x to 438.x codes.
2. End Stage Renal Disease (ESRD) is defined by any of ICD-9-CM 250.3x, 585.x, 586.x, or an estimated Glomerular Filtration Rate (eGFR)  $<15\text{mL/min}/1.73\text{m}^2$ , according to the definition of the National Kidney Foundation.
3. Mortality is defined by a documented death in the Hong Kong Death Registry.

The definitions of each HT complication are determined by the clinician co-investigators and endorsed by clinicians of the HA.

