**Long Term Effectiveness of RAMP-HT**

Descriptive statistics will be performed on the clinical parameters (e.g. blood pressure (BP), lipid profile, BMI) and incidence of CHD, heart failure, stroke, ESRD, HT-related mortality and all-cause mortalities of the RAMP-HT and usual care cohorts. Differences in each outcome between groups will be tested using independent t-tests for continuous variables such as mean BP, or chi-square tests for categorical variables such as proportion of patients with BP control or CVD incidence. The number needed to treat to reduce one CVD, each specific HT complication and death by RAMP-HT will be calculated from the unadjusted 5-year rates between RAMP-HT and usual care HT cohorts.

Multivariable Cox proportional hazards regression will be performed to estimate the adjusted effect of RAMP-HT on the dependent variable of each first HT complication event, adjusting for all baseline covariates of patients. Cox model has been widely used to evaluate the effectiveness of primary care intervention in previous study. For each model, survival curves will be estimated by Kaplan-Meier method and the differences between RAMP-HT and usual care groups will be compared using the

log-rank test. The effectiveness of RAMP-HT will be measured by Hazard ratio with 95% confidence intervals in the regression models. Predictive accuracy of Cox models will be assessed and compared using Harrell's discrimination C-index, ranging from zero to one. A value of 0.5 indicates no predictive discrimination, and values of 0 or 1.0 indicate perfect separation of patients. Goodness-of-fit for Cox regression model will be assessed using Akaike information criterion and Bayesian information criterion.

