3. HT patients with complications may die from either HT-related death or other cause of death.
4. RAMP-HT is effective in reducing HT complications for a period of 5 year; thus the transition probability adjustment of CVD/ESRD development (as determined by the annualized hazard ratio obtained from our long-term effectiveness analysis) will be applied to the model of the RAMP-HT cohort in the first five years. After 5 years, the RAMP-HT will have the same transition probabilities of developing HT complications as usual care HT cohort.
5. RAMP-HT is repeated every 12-24 months and the effectiveness of RAMP-HT will not decrease over time; thus the 5-year effect of RAMP-HT can be annualized. Adjustment will be made on the average duration of repeat RAMP-HT based on available empirical data in order to avoid over-estimation of the RAMP-HT cost.
6. The medical cost (public and private) of HT patients in usual care and RAMP-HT programme is the same for the same HT health status except for the additional RAMP-HT cost.
7. All costs and health preference will be discounted by an annual rate of 3.5% as recommended by the guidance of National Institute for Health and Clinical Excellence (National Institute for Clinical Excellence 2008).

[Word Count: 3968 ]

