**f) Existing Facilities:**

The Department of Family Medicine and Primary Care (FMPC) has more than 20 years of experience in health services research with a focus on quality of primary care and patient-reported outcomes. Our research team of clinical academic staff, postdoctoral fellows, statisticians and research assistants has a track record of close collaboration with the HA in the extraction and analysis of longitudinal data from the HA CMS in the past five years in the evaluation of QOC studies of various enhanced primary care programmes including the RAMP-HT, RAMP-DM and Patient Empowerment Programme (PEP) which involved over 400,000 patients and have published 10 papers from these studies.

*Relevance of Past Studies Conducted*

As explained above, we have already identified the required cohort of over 16,000 HT patients and will have collected their 3-year clinical data by 30 November 2015, which provides an opportunity for an extended 5-year study. Our research team in the Department of Family Medicine and Primary Care in collaboration with our School of Public Health and School of Nursing also has a track record of cost-effectiveness analysis studies including an on-going in-depth study of the cost-effectiveness of the RAMP-DM and PEP to be completed in 2016.

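### Usual care is restricted to patients who never join RAMP-HT up to the last day of follow-up, which likely overstates usual-care mortality and leaves the primary CVD comparison open to bias of unknown sign

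*Combined protocol and SAP*

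**What the plan says.** In section d(ii), Subjects, usual-care patients are those "who have never enrolled into RAMP-HT on or before 31 March 2017, fulfilled the following inclusion criteria". The RAMP-HT cohort needs only enrolment between 1 October 2011 and 31 March 2012; nothing is required of its later status.

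Inclusion criterion 2 sets baseline as "date of RAMP-HT enrolment for RAMP-HT cohort, and 31 March 2012 for usual care cohort". Under HA CMS Data Extraction, each patient "will be observed from baseline to the first occurrence of any of the outcome events until 31 March 2017". The CVD definition there covers fatal events: "CHD includes all ischaemic heart disease, myocardial infarction (MI), coronary death or sudden death", and fatal stroke.

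Propensity matching and Cox adjustment use baseline covariates. The NNT "will be calculated from the unadjusted 5-year rates between RAMP-HT and usual care HT cohorts". Markov assumption 4 adjusts the RAMP-HT transition probabilities for the first five years, "as determined by the annualized hazard ratio obtained from our long-term effectiveness analysis".

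On the cohort itself, Sample size calculation (item a) states: "We have identified from the HA CMS data set of the RAMP-HT QOC study 8,681 eligible RAMP-HT patients and 8,681 usual care patients". It adds that these matched cohorts will be the study subjects. Existing Facilities says "we have already identified the required cohort of over 16,000 HT patients". Neither place says how a condition running to 2017 was applied to them.

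**The concern.** Entry to the comparator depends on five years of information gathered after baseline, over exactly the window in which outcomes are counted. Death makes later enrolment impossible, so every usual-care death is retained, while survivors who enrol are dropped together with their event-free time. The RAMP-HT arm undergoes no such filtering.

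Matching and covariate adjustment can rebalance joining that depends on measured baseline risk. They cannot remove the dependence created by death preventing joining. The plan contains no censoring at joining, no time-varying exposure and no sensitivity analysis for this.

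At stake is the mortality part of Hypothesis 1: the rule can yield an apparent survival benefit when the programme has none. The CVD and ESRD comparisons are exposed too, but less directly. Fatal CVD blocks joining. Non-fatal CVD or ESRD causes bias only if the event changes the chance of joining, or if joining depends on risk that the match misses.

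**Working it through.** The plan gives no figure for later joining or for mortality, so there is nothing of its own to reproduce on this point. What follows is an illustration.

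**Inputs from the plan:** 5-year window for usual care (31 March 2012 to 31 March 2017); 5-year CVD incidence of 8% in usual care and 7% in RAMP-HT, and 8,681 per group (Sample size calculation); two-sided 5% tests.

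**Assumed inputs:** joining at 2, 5 or 10% per year (9.5, 22 or 39% over five years, from 1 − exp(−5r)); true 5-year mortality 5%; 10 or 20% of CVD events fatal; no programme effect.

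**Formulas.** With event hazard l, joining hazard r and T = 5:
- l = −ln(1 − p)/5
- retained event-free = exp(−T(l + r))
- retained events, if the event blocks joining = l/(l + r) × (1 − exp(−T(l + r)))
- retained events, if it does not = exp(−rT) × (1 − exp(−lT))
- apparent risk = retained events / (retained events + retained event-free)
- spurious HR (RAMP-HT against usual care) = ln(1 − p true)/ln(1 − p apparent)

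**Mortality, 5% per year joining.** l = −ln(0.95)/5 = 0.010259. Deaths retained = 0.010259/0.060259 × (1 − exp(−0.30129)) = 0.04429. Survivors retained = exp(−0.30129) = 0.73986. Apparent risk = 0.04429/0.78415 = 5.65%. HR = ln(0.95)/ln(0.9435) = 0.88.

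| Joining per year | Apparent mortality | Spurious HR | Spurious NNT | Chance that a two-sided test favours RAMP-HT |
|---|---|---|---|---|
| 2% | 5.25% | 0.95 | about 405 | about 11% |
| 5% | 5.65% | 0.88 | about 154 | about 48% |
| 10% | 6.40% | 0.77 | about 71 | about 98% |

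The NNT is 1/(apparent − 0.05). The last column uses the pooled two-proportion normal formula with 8,681 per group. At a true mortality of 3% or 8% the HRs barely change.

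**Mortality, unequal risk.** Let 30% of patients have double the hazard and join three times as often. The HR is 0.96/0.91/0.83 if matching misses that risk and 0.94/0.86/0.73 within matched risk groups. A more extreme unmeasured pattern (10% of patients, tenfold hazard, fivefold joining) brings the HR to about 1.01 at 5% per year.

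**Mortality, rule applied for part of follow-up.** If joining removes patients only in the first 3.67 years (to November 2015), the HR is 0.97/0.93/0.87; if only in the first year, 0.998/0.995/0.990.

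**Composite CVD, true risk 8%, only fatal events block joining.** HR at 2/5/10% per year:

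| Scenario | 10% of events fatal | 20% of events fatal |
|---|---|---|
| Equal risk | 0.99/0.99/0.97 | 0.99/0.97/0.95 |
| 30% with double hazard and triple joining, captured by matching | 0.99/0.98/0.96 | 0.99/0.97/0.93 |
| Same, not captured by matching | 1.01/1.03/1.06 | 1.01/1.02/1.03 |

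The sign changes between the second and third rows, and the documents do not say which row applies.

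**The case against.** Four points deserve weight.

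First, a reader might infer that the primary CVD result is biased in favour of RAMP-HT. The documents do not support that. The Introduction says the programme was aimed at uncontrolled hypertension, so later joining may follow persistently poor control after baseline, which baseline matching cannot see. In that case the composite bias can run against RAMP-HT, as the last table row shows. This objection stands.

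Second, the large figures concern a secondary outcome, and a reader might carry them over to the ICER. The Markov section takes complication mortality from the literature and other-cause mortality from the life table, so the mortality bias largely bypasses the model. Exposure there is mainly through the CVD and ESRD hazard ratios. The 98% figure requires 10% joining per year, which nothing in the documents supports or excludes. This also stands.

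Third, the 8,681 pairs already existed, so the 2017 condition may have shaped them only in part or not at all. That limits the size but does not settle the matter: the written criterion could not yet have been fully applied, and the plan does not say which version will be analysed. The November 2015 date is when 3-year data become available, not a stated selection date.

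Fourth, keeping joiners in usual care puts programme exposure into the comparator and dilutes the hazard ratio that the Markov model uses. That is a fair objection to prescribing one analysis, but not to fixing eligibility at baseline.

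**Conclusion.** The criterion is wrong as written and needs correcting before the final analysis. For all-cause mortality, bias in favour of RAMP-HT is likely: a spurious HR of about 0.95 to 0.77 for 2 to 10% joining per year with equal risk. It is nil without later joining, smaller if the rule covered only part of follow-up, and offset only by a strong unmeasured concentration of joining among high-risk patients. Both the joining rate and the mortality are assumptions.

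For composite CVD the comparison is exposed, but the sign is unknown: HR about 0.93 to 0.99 if matching captures the risk that drives joining, and about 1.01 to 1.06 in the stated scenario if it does not. Neither size nor sign can be settled for ESRD or the ICER from the documents.

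**What to change.** - Define usual care by status at baseline: not enrolled in RAMP-HT by 31 March 2012. Re-run the 1:1 match and obtain joining dates from the CMS.
- Pre-specify how later joiners are handled: either kept in usual care to the end of follow-up, or censored at joining with inverse-probability-of-censoring weights from time-updated CMS data. Make one the main analysis and the other the sensitivity analysis, at the sponsor's choice. State the estimand and make it consistent with the hazard ratio used in Markov assumption 4.
- Report how many usual-care patients joined later.
- Reconcile Sample size calculation with Subjects by stating whether the 8,681 pairs were selected under the 2017 rule and, if so, up to what date.

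The cost is one reworded criterion, one re-extraction and one re-match. The Timeline places the final extraction and analysis in April to November 2017.

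If joiners are kept and are assumed to gain the full benefit at once, their hazard switches from −ln(0.92)/5 to −ln(0.93)/5 at joining. Usual-care CVD incidence then falls from 8% to about 7.95, 7.885 or 7.79% at 2, 5 or 10% per year, against 7%. Two-sided power at 8,681 per group drops from about 71% to about 66, 60 or 51%. The 71% comes from the standard two-proportion formula; the plan's claim of 90% power at 7,116 per group does not reproduce with that formula (14,577 per group needed), which is a separate matter.

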#### Inclusion criteria

1. Age  $\geq 18$  years old and  $<80$  years old
2. Coded with ICPC-2 of K86 on or before baseline\* (\*date of RAMP-HT enrolment for RAMP-HT cohort, and 31 March 2012 for usual care cohort)
3. Had uncontrolled blood pressure (i.e. average Systolic Blood Pressure (SBP)  $\geq 140$  mmHg OR Diastolic Blood Pressure (DBP)  $\geq 90$  mmHg between 6 months before and 3 months after baseline\*)

#### Exclusion criteria

1. Patients who had a diagnosis of any HT complications defined by relevant ICPC-2 and/or ICD-9-CM diagnosis codes (defined in the "Methods" section) on or before baseline\*
2. Patients diagnosed to have Diabetes Mellitus (DM) on or before 31 March 2017, defined by ICPC-2 codes of T89 or T90
3. Patients exclusively managed by Specialist Out-Patient Clinic (SOPC) on or before baseline\*

To reduce selection bias, the RAMP-HT and usual care subjects will be matched in baseline covariates using the propensity score matching method:

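### The diabetes exclusion runs to the last day of follow-up, so entry to both cohorts depends on a post-baseline event that may differ by arm

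*Combined protocol and SAP*

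**What the plan says.** The second item under Exclusion criteria removes "Patients diagnosed to have Diabetes Mellitus (DM) on or before 31 March 2017, defined by ICPC-2 codes of T89 or T90". Item 1 (existing hypertension complications) is tied to baseline, and so is item 3: "Patients exclusively managed by Specialist Out-Patient Clinic (SOPC) on or before baseline".

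Baseline is defined under Inclusion criteria as "date of RAMP-HT enrolment for RAMP-HT cohort, and 31 March 2012 for usual care cohort", and RAMP-HT enrolment runs from 1 October 2011 to 31 March 2012. In the section on CMS data extraction, each patient "will be observed from baseline to the first occurrence of any of the outcome events until 31 March 2017". The diabetes cut-off and the end of outcome follow-up are therefore the same day.

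The Subjects section applies the criteria to both arms. RAMP-HT patients who "fulfilled the following inclusion criteria and without any exclusion criterion will be included in the RAMP-HT cohort", and the same condition is set for usual care.

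The Sample size section states that the study team has already identified "8,681 eligible RAMP-HT patients and 8,681 usual care patients who fulfilled the inclusion criteria and without any exclusion criterion", matched by propensity score. The plan gives no reason for the 2017 date, no rule for censoring at diabetes onset, and no sensitivity analysis that keeps incident diabetes.

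**The concern.** Eligibility for a cohort should be decided from what is known at time zero. Here it is decided partly by what happens during the following five years, with three consequences.

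First, outcome events can be erased by a later diagnosis, and survival affects who can be erased.

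Second, the population changes. Objective 1 concerns primary care patients with uncontrolled hypertension at baseline. The rule replaces them with patients who are never coded with diabetes over the next five years, a group that no clinic can recognise at enrolment.

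Third, the deletion may depend on treatment. The Introduction says of RAMP-HT: "Standardized cardiovascular risk factor assessment, hypertensive complication screening and assessment on patient adherence to treatment are carried out on enrolled patients". It adds that a team including dieticians and physiotherapists then manages each patient's risk factors. Closer assessment could raise the rate of diabetes coding, and risk-factor management could lower onset. Either would remove high-risk patients at different rates in the two arms.

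At stake are 5-year CVD incidence, the hazard ratios and the NNT, which is taken from unadjusted rates. The ICER is also exposed, because the hazard ratio adjusts the Markov transition probabilities for the first five years.

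**Working it through.** **Timing.** From 31 March 2012 to 31 March 2017 is 5 years; from 1 October 2011 it is 5.5 years. Exclusion 2 therefore looks 5 to 5.5 years past baseline, and exclusions 1 and 3 look no further than baseline.

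**Effect on individual patients, all free of diabetes at baseline.**

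| History | Under exclusion 2 |
|---|---|
| CVD in year 2, diabetes code in year 3 | Deleted, CVD event lost |
| No CVD, diabetes code in year 4 | Deleted, all event-free time lost |
| Death in year 1 | Cannot be coded later, retained |

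**Can the analysis repair it?** The propensity score uses baseline covariates, and the Cox model adjusts for baseline covariates. Neither acts on selection that happens after baseline.

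**Size.** The documents give no diabetes incidence and no coding rates, so there is no plan figure to reproduce. The benchmark is the planned difference in the Sample size section: 8% − 7% = 1 point. Everything else here is assumed:

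- no true effect, with 5-year CVD of 8% in both arms (the plan's usual-care figure);
- a share D develops diabetes, with k times the CVD risk of the others;
- a share s of those is coded and deleted, independently of CVD.

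CVD risk without diabetes is r = 0.08 / (1 − D + kD).

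CVD among those retained is [r(1 − D) + k·r·D(1 − s)] / (1 − Ds).

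With D = 10% and k = 2, r = 0.08 / 1.10 = 7.27%.

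*Detection route* (more diabetes coded under RAMP-HT):

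| Coded, RAMP-HT vs usual care | RAMP-HT | Usual care | False difference favouring RAMP-HT |
|---|---|---|---|
| 70% vs 70% | 7.51% | 7.51% | 0 |
| 80% vs 70% | r × 0.94/0.92 = 7.43% | r × 0.96/0.93 = 7.51% | 0.08 points |
| 90% vs 60% | 7.35% | 7.58% | 0.23 points |
| 100% vs 50% | r × 0.90/0.90 = 7.27% | r × 1.00/0.95 = 7.66% | 0.38 points |

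At 80% versus 70%, about 8,681 × 0.08 = 694 RAMP-HT and 8,681 × 0.07 = 608 usual-care patients would be deleted. Varying D from 5% to 15% and k from 1.5 to 3, with coding of 80% versus 70% or 90% versus 60%, gives 0.02 to 0.60 points.

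*Prevention route* (RAMP-HT lowers onset). Assume 20% are at high risk of diabetes, with doubled CVD risk, so r = 0.08 / 1.20 = 6.67%. Of these, 50% convert and are coded under usual care: r × 1.00/0.90 = 7.41%.

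- 40% convert under RAMP-HT: r × 1.04/0.92 = 7.54%, a false difference of 0.13 points against RAMP-HT.
- 30% convert under RAMP-HT: r × 1.08/0.94 = 7.66%, 0.25 points against.

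With k from 1.5 to 3, the range is 0.07 to 0.43 points against.

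**The 8,681 pairs.** The plan expects 3-year data by November 2015, and the Timeline puts the 5-year extraction in April to November 2017. A rule that needs codes up to 31 March 2017 cannot have been fully applied to pairs already described as free of every exclusion criterion.

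**The case against.** **The mechanism is inferred.** No glucose test or diabetes screening is named in the text supplied, and the programme appendices are not part of it. Diet, exercise and weight reduction appear in the Introduction as general treatments for hypertension, not as listed content of RAMP-HT. Usual-care patients attend the same public clinics and also have lipid and BMI data. This stands: an effect on detection or onset is plausible, not documented.

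**A large bias favouring RAMP-HT.** A reader might infer this from the 0.38-point figure. It needs every case coded in one arm and half in the other, which nothing in the documents supports. A 10-percentage-point gap in coding gives 0.08, and prevention reverses the sign.

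**Broken pairs.** A reader might also infer that pairs will be broken one member at a time. The plan does not say so. The Subjects section describes selection in the future tense, and matching could be re-run once the 2017 data arrive. The planned tests are unpaired in any case.

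**A possible reason for the date.** The documents mention a parallel diabetes programme, RAMP-DM, and Table 1 has no diabetes state for transitions, costs or utilities. Excluding incident diabetes keeps diabetes care out of the state for hypertension without complications. The plan does not state this rationale. It is a real trade-off, but it does not justify deleting follow-up and events that came before the diagnosis.

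None of these points removes the dependence on a post-baseline event or the change of population.

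**Conclusion.** The criterion is wrong as written. That entry depends on diabetes codes up to the end of follow-up, and that the cohort then differs from the one in Objective 1, follows from the text alone.

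Whether deletion differs by arm is an inference, and the size and sign of any bias in the treatment comparison are unknown. With no true effect, 10% developing diabetes and doubled CVD risk, the detection route gives 0.08 to 0.38 points favouring RAMP-HT across the unequal scenarios shown. It gives zero if detection and onset are equal. The prevention route runs the other way. Against a planned difference of 1 point, this could be negligible or material.

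The documents do not support saying that the result is biased towards RAMP-HT, or that the programme is known to screen for or prevent diabetes.

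**What to change.** 1. Change exclusion 2 to diabetes coded on or before baseline, in line with exclusions 1 and 3.
2. State which diabetes cut-off was used to form the 8,681 pairs. Confirm the selection, or re-run it, on the baseline definition.
3. Keep patients with later diabetes in their cohort for all outcomes.
4. If the effect without later diabetes is of interest, censor at diagnosis in a sensitivity analysis only. State that this censoring may be informative and may differ by arm.
5. Report costs with and without incident diabetes.

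The cost is one date, a check or re-run of selection, and an extra cost breakdown. The downside is that some follow-up and costs will include diabetes care, which the Markov model has no state to hold; hence step 5.

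Two limits remain. Diabetes coded at an enrolment-day assessment would still be excluded in the RAMP-HT arm only. The separate condition that usual-care patients never enrol in RAMP-HT up to 31 March 2017 is also post-baseline, and this change leaves it in place.
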